8.2.5.3 Summaries of Baseline Characteristics, Demographics, and Other Analyses

The comparability of the treatment groups at baseline for each relevant characteristic will be assessed by the use of tables and/or graphs. No statistical tests will be performed on these characteristics. The number and percentage of subjects screened, randomized, the primary reasons for screen failure, and the primary reason for discontinuation will be displayed. Medical history and prior and concomitant therapies will be summarized by treatment either by descriptive statistics or categorical tables. In addition, the following demographic/ anthropometric, diabetes-related, and baseline efficacy variables will be summarized by treatment either by descriptive statistics or categorical tables. Depending on the variable of interest, statistics such as sample size, mean, SD, median, range and proportion will be provided.

- Continuous baseline demographic variables: age (years), weight (kg) and height (cm)
- Baseline BMI, and distribution of at baseline BMI ($<25, \ge25$ to $<30, \ge30$ to $<35, \ge35$ kg/m²)
- Categorical baseline demographic variables: age (<65 years, ≥65 years), gender (male, female), and race (White, Black, Asian, American Indian or Alaska Native, Native Hawaiian or Other Pacific Islander, or Multi-Racial), ethnicity (Hispanic/Latino or not).
- Baseline A1C, and distribution of A1C at baseline ($\leq 8, \geq 8$ to $\leq 9, \geq 9\%$)
- Baseline FPG
- Time since diagnosis of diabetes mellitus (years) ($<5, \ge 5$ to $<10, \ge 10$ years)
- AHA washout status (Yes, No)

The above summaries will be provided for all subjects who received at least one dose of study therapy.

8.2.6 Multiplicity

The Type-I error rate over the multiple treatment comparisons (i.e., two MK-8521 doses versus placebo) for the primary hypothesis will be controlled by an ordered testing procedure. This testing procedure will first test the 300 μ g dose. If a statistically significant result is observed, then the 180 μ g dose will be tested and the primary hypothesis test will be considered successful, regardless of the outcome of the 180 μ g vs. placebo.

In the event that fewer than 75% of the subjects in the 300 μ g dose group receive the full target dose, the first test of MK-8521 vs. placebo will be performed at the 180 μ g dose. If the 180 μ g dose vs. placebo is statistically significant, then the primary hypothesis will be considered successful.

The secondary hypotheses for body weight and FPG are deemed supportive and will only be tested if significance is achieved at the corresponding dose level for A1C.

Comparisons involving other efficacy endpoints and other treatment comparisons (MK-8521 doses vs. liraglutide) are considered supportive or exploratory and will be made at α =0.05

Protocol/Amendment No.: 004-02

nominal level (two-sided) and 95% CIs will be provided. No multiplicity adjustment will be performed for these other comparisons.

From a safety standpoint, application of a multiplicity adjustment could potentially mask a safety concern. No multiplicity adjustment is planned for safety endpoints.

An interim analysis will be performed to assist in program planning, support sample size reestimation, and support assessment of whether the study should be terminated based on an assessment of the overall data and in consideration of programmatic goals (described in Section 8.2.9). This is not a pivotal trial and the trial will not be stopped early for positive results. Therefore, no alpha adjustment will be made for this interim analysis.

8.2.7 Sample Size and Power Calculations

After 12 weeks of MK-8521, a reduction of $\geq 0.8\%$ in A1C and ≥ 2 kg in body weight, relative to placebo, is expected.

A total of approximately 160 subjects will be randomized in a 1:1:1:1 ratio to 300 µg dose and 180 µg dose of MK-8521, placebo or liraglutide. A sample size of 40 subjects per arm will provide approximately 85% power to detect a treatment difference of 0.8% in A1C reduction at Week 12 (alpha=0.05, two-sided test). The half-width of the 95% CI of A1C is 0.52%. This calculation is based upon the following assumptions:

- 1. Cumulative attrition rates at Weeks 6 and 12 are 0.08 and 0.16, respectively.
- 2. The conditional standard deviation is 1.1%.
- 3. The conditional correlation between Weeks 6 and 12 is 0.76732.

The correlation between Weeks 6 and 12 is derived based on data from MK-0431 PN020. The high attrition rates are used to account for dropout risks due to the requirement of taking 2 subcutaneous injections daily and any potential AEs in this first outpatient trial of MK-8521. The SD is assumed to be 1.1% to account for more variability in patients with higher baseline A1C. The sample size of 40 subjects will be equivalent to an effective sample size of 35 subjects at Week 12, which accounts for information loss due to missing data and correlation among repeated measures and is derived using the method proposed by Lu, et al. [24].

The sample size of 40 subjects per arm will provide approximately 87% power to detect a treatment difference of 2 kg in body weight loss at Week 12. The half-width of the 95% CI of body weight is 1.23 kg. This calculation is based on the same dropout rates and correlation for the A1C and on the conditional standard deviation of 2.7 kg.

The sample size of 40 subjects per arm will provide approximately 88% power to detect a treatment difference of 30 mg/dL in FPG at Week 12. The half-width of the 95% CI of FPG is 18.9 mg/dL. This calculation is based on the same dropout rates and correlation for the A1C and on the conditional standard deviation of 40 mg/dL.

Protocol/Amendment No.: 004-02

8.2.8 Subgroup Analyses

To assess whether the treatment effect at Week 12 is consistent across various subgroups, the between-group treatment effect (with a nominal 95% CI) for A1C and body weight will be estimated and plotted within each category of the following classification variables:

- Gender (female or male)
- Age (> or \leq median)
- Stratification A1C (<8.5% or $\ge 8.5\%$)
- Stratification BMI ($<30 \text{ or } \ge 30 \text{ kg/m}^2$)
- AHA washout status (Yes, No)
- Prior GLP-1 (Yes or No)

The consistency of the treatment effect will be assessed in the context of the primary efficacy analysis model. In the case of subgroups that are defined by terms that are in the primary analysis model, the term that confounds with the subgroup factor will be excluded from the subgroup analysis model. Treatment effects and nominal 95% CIs by category for the classification variables listed above will be reported as well as presented graphically. Formal statistical testing of treatment-by-subgroup interactions will not be performed for other subgroup factors.

The treatment effect across study centers will be summarized for A1C at Week 12 with descriptive statistics.

Results from the subgroup analyses should be reviewed cautiously. Because sample sizes within subgroups will be smaller than the overall study sample size, estimation may not be precise and 95% CIs will usually be wide in the subgroup analyses.

8.2.9 Interim Analyses

8.2.9.1 Triggered Safety Review for Discontinuation Due to HR

In the event of ≥ 5 subjects discontinuing blinded investigational product (MK-8521 or matching placebo) due to meeting the defined discontinuation criteria for an increase in HR, a review of unblinded safety data by a Standing Internal Data Monitoring Committee will be triggered. For further details on the siDMC, see Section 7.3.2. Review criteria will be provided in the siDMC charter.

8.2.9.2 Planned Efficacy and Safety Review

An interim analysis will be performed when at least 50% subjects have completed the Week 12 Visit or discontinued prior to the Week 12 Visit, to assist in program planning, support sample size re-estimation, and support assessment of whether the study should be terminated based on an assessment of the overall data and in consideration of programmatic goals. The treatment-level results will be reviewed by the siDMC. This is not a pivotal trial and the trial will not be stopped early for positive results. Therefore, no alpha adjustment will be made for this interim analysis.

If interim data are considered to warrant consideration for administrative action with regard to other aspects of the development program, the unblinded interim data will be reviewed

Protocol/Amendment No.: 004-02

with additional individuals with programmatic oversight. Individuals directly involved with study conduct will not be unblinded.

For the interim efficacy analysis, the Full Analysis Set (FAS) population will be used as described in Section 8.2.4.1. Additional analyses based on the per-protocol population and the modified FAS population will be performed.

The efficacy of the MK-8521 treatment groups will be assessed using the same analysis approach described in Section 8.2.5.1 and the key endpoints are outlined in Table 14. Study termination at the interim analysis will be considered if either of the following criteria is met for both doses of MK-8521:

- A1C futility criterion: Potentially terminate the study for futility if the lower bound of the 95% CI for the treatment difference (MK-8521 minus liraglutide) in change from baseline is above 0.
- Body weight futility criterion: Potentially terminate the study for futility if the
 posterior probability is < 5% that the true placebo-adjusted weight loss with MK8521 is at least 4.5 kg.

The futility criteria will be non-binding. If either criterion is met, the unblinded interim data will be reviewed with additional individuals with programmatic oversight and the decision to terminate or continue the study will be made based on assessment of the overall data and in consideration of programmatic goals.

Details including safety endpoints (AEs and change from baseline in heart rate) and review criteria will be provided in the siDMC charter.

Power and sample size will be re-assessed based only on the conditional standard deviation at the interim analysis and will be performed by the unblinded statistician. If any sites are identified as having low compliance as defined in Section 8.2.4, the goal of the sample size adjustment will be to ensure adequate power in the mFAS population. The conditional standard deviation for A1C and body weight will be estimated from the cLDA model in the mFAS population. Implementation details will be provided in the siDMC charter.

As stated in Section 8.2.7, the initial sample size (40 per arm) will provide 85% power for the A1C hypothesis and 87% power for the body weight hypothesis, resulting in 74% overall power for success in testing both hypotheses. The sample size will be increased, if necessary, so that there is at least 80% power for each individual hypothesis for A1C and body weight, and at least 74% overall power for both hypotheses in the mFAS population. A conservative estimate of SD will be used to calculate the power and sample size. The following rules will be used for adjusting the sample size:

- For A1C, 0.1% will be added to the point estimate of conditional SD from the interim data. For example, if the point estimate is 1.1%, 1.2% will be used in the sample size computation;
- For body weight, 0.2 kg will be added to the point estimate of conditional SD from the interim data. For example, if the point estimate is 2.7 kg, 2.9 kg will be used in the sample size computation.

Protocol/Amendment No.: 004-02

If necessary, the sample size will be increased to the minimum sample size that meets the power criteria above, subject to a maximum of 45 subjects per arm in the mFAS population and a total maximum of 200 subjects randomized. If the power criteria above cannot be met within these sample size constraints, the trial will continue using the maximum permissible sample size under these constraints.

Table 14 Summary of Planned Efficacy and Safety Interim Analysis Strategy

Key Endpoints for Interim Analysis	Timing of Interim Analysis	Purpose of Interim Analysis	
Change in body weight at week 12	When at least 50% of randomized subjects either	 Program planning Sample size re-	
C1 : IID : W 1 12		estimation, • Study termination for futility.	

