8.2.4 Analysis Populations

8.2.4.1 Efficacy Analysis Populations

The Full Analysis Set (FAS) population will serve as the primary population for the analysis of efficacy data in this study. The FAS population includes subjects who take at least one dose of study therapy and have at least one efficacy measurement either at baseline or during the treatment period. Subjects will be included in the treatment group to which they were randomized.

A secondary population for analyzing primary and key secondary efficacy endpoints at Week 12 will be the Per-Protocol (PP) population. All randomized subjects who take at least one dose of study medication, with a measurement at baseline and the time point of interest (Week 12), without the protocol deviations described below will be included in this population.

Protocol deviations used to determine the PP population are not just a repetition of the exclusion and inclusion criteria in the protocol, but a clinical assessment of deviations from the protocol-specified criteria that will either affect or confound the measures of efficacy. The following rules define protocol violators during the trial period of interest (Day 1 through Week 12) and will be used to identify such subjects prior to unblinding. Subjects with any of the following violations will be excluded from the PP population at all time points.

- **Drug compliance:** A subject will be excluded from the PP population due to low compliance if either of the following applies:
 - Compliance assessed by prime therapy records provided by the investigator in the eCRF is <90%.
 - <75% of evaluable trough PK samples have quantifiable concentrations. This
 criterion is applicable only to subjects in the MK-8521 and liraglutide groups.
 

Protocol/Amendment No.: 004-02

Additionally, a site will be deemed to have low compliance and all subjects from that site (including those randomized to the placebo group) will be excluded from the PP population if either of the following applies:

- o For sites with exactly 2 subjects randomized to active groups, both of these subjects have low compliance based on trough PK criterion noted above.
- o For sites with 3 or more subjects randomized to active groups, ≥50% of subjects have low compliance based on the trough PK criterion noted above.
- Use of prohibited medications: The list of prohibited medications can be found in Section 5.5.

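### Does the sample-size re-estimation rule contradict itself by raising enrolment when the interim SDs match the plan, and by setting its power target in mFAS?

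*Combined protocol and SAP*

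**What the plan says.** Section 8.2.7 plans the trial as follows: "A total of approximately 160 subjects will be randomized in a 1:1:1:1 ratio". With 40 per arm it claims "approximately 85% power to detect a treatment difference of 0.8% in A1C reduction at Week 12" ("alpha=0.05, two-sided test"), and 87% power for a 2 kg difference in body weight. The conditional SDs are 1.1% and 2.7 kg, and dropout reduces 40 per arm to an effective 35.

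Section 8.2.9.2 combines these into 74% power for both hypotheses. At the interim the sample size is raised if needed to secure "at least 80% power for each individual hypothesis for A1C and body weight, and at least 74% overall power for both hypotheses". The SDs used are deliberately enlarged: "if the point estimate is 1.1%, 1.2% will be used in the sample size computation" and "if the point estimate is 2.7 kg, 2.9 kg will be used in the sample size computation". The increase is "subject to a maximum of 45 subjects per arm in the mFAS population" and to 200 randomized in total. If the criteria cannot be met within those limits, the trial continues at the largest size they allow.

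The criteria apply to mFAS, and the stated reason is the possible identification of low-compliance sites. For the analysis itself, section 8.2.4.1 says: "The Full Analysis Set (FAS) population will serve as the primary population for the analysis of efficacy data in this study". It lists mFAS as an additional secondary population.

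**The concern.** The 74% joint target is what 40 per arm delivers at exactly 1.1% and 2.7 kg. Adding a margin to the SDs before checking that same target means an interim that confirms the plan must fail the check. The worked examples in section 8.2.9.2 use the planning SDs themselves, and even the 45-per-arm cap does not reach 74% for them. The rule then resembles an automatic increase more than a test of the variance assumption, while section 8.1.3 says only that the size may be increased.

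The second worry is the population. Power is targeted in mFAS, but the hypotheses are decided in FAS. If excluded sites contain subjects who took little drug, the deciding test could have less power than the figure the rule aims at.

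**Working it through.** **Inputs.** From section 8.2.7: two-sided alpha 0.05; differences 0.8% and 2 kg; SDs 1.1% and 2.7 kg; cumulative attrition 0.08 and 0.16; correlation 0.76732; effective n 35 of 40 (ratio 0.875). From section 8.2.9.2: add-ons 0.1% and 0.2 kg; caps of 45 per arm and 200 in total; joint power taken as the product of the two powers.

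**Formula.** Power ≈ Φ(δ / (SD·√(2/n)) − 1.96), with n the effective size per arm. Ranges below also cover a noncentral t calculation and a second conversion to effective n. That conversion uses the variance factor 0.76732²/0.92 + (1 − 0.76732²)/0.84 = 1.130, so 40/1.130 = 35.4.

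**The plan's own figures (40 per arm, n = 35).**
- A1C: 0.8/(1.1·√(2/35)) = 3.04, power 86% (85% by t). Stated: 85%.
- Body weight: 2/(2.7·√(2/35)) = 3.10, power 87% (86% by t). Stated: 87%.
- Joint: 0.85 × 0.87 = 0.74. Recomputed: 73–76%.

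The plan's figures reproduce.

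**The rule when the interim SDs equal the planning SDs.** The check uses 1.2% and 2.9 kg.

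| Per arm | A1C | Weight | Joint |
|---|---|---|---|
| 40 | 78–80% | 81–83% | 64–66% |
| 45 | 83–85% | 86–87% | 71–73% |

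A joint 74% needs about 46–48 per arm. As a rough check, 40 × (1.2/1.1)² = 47.6 and 40 × (2.9/2.7)² = 46.1. By the normal approximation, 40 per arm passes only if the interim SDs come out near 1.0% and 2.5 kg. If the true SDs are exactly 1.1% and 2.7 kg, simulation puts the chance of no increase at about 3–14%. This assumes 60–140 degrees of freedom for each SD estimate and independence of the two estimates; neither assumption is in the documents.

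**Actual power if 1.1% and 2.7 kg are the true SDs.**

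| Per arm | A1C | Weight | Joint |
|---|---|---|---|
| 40 | 85–86% | 86–88% | 73–76% |
| 45 | 89–90% | 90–91% | 80–82% |

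The increase is 4 × 45 − 160 = 20 subjects if no site is excluded.

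**Dependence on the product rule.** At 45 per arm and the inflated SDs, the normal approximation gives joint power of 72.7% at correlation 0, 73.9% at 0.2 and 74.5% at 0.3 between the two test statistics. A correlation of about 0.22 meets the target. Section 4.2.3.1 expects weight loss to contribute to A1C reduction, so some positive correlation is plausible.

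**FAS against mFAS (assumed scenarios, normal approximation).** Take 45 per arm in mFAS plus 5 per arm at excluded sites, with SDs 1.2% and 2.9 kg; mFAS power is 84.1% and 86.4%.
- Excluded subjects have no effect: the FAS difference in A1C is 0.8 × 45/50 = 0.72, and FAS power is 80.1% (A1C) and 82.7% (weight).
- Excluded subjects have half the effect: the difference is 0.8 × 0.95 = 0.76, and FAS power is 84.2% and 86.5%, equal to mFAS.

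A harsher case has 20% of 200 subjects at sites with no effect and SDs 1.1% and 2.7 kg. It gives FAS about 77% and 79% against mFAS 86% and 87%. With half the effect retained, FAS returns to 86% and 87%.

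**The case for a change.** The strongest case for a change is that the target, the margin and the cap do not fit together. A reader of section 8.1.3 would not learn that an increase is the expected outcome when the planning SDs are right. With 47 per arm the total is 188, inside the 200 ceiling, so where no sites are excluded only the 45-per-arm limit blocks the target.

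Those facts stand, but they describe a cautious rule, not a broken one. The SDs are expressly called conservative, and adding a margin to an SD estimated from about half the data protects against underestimation. The rule still responds to variance: were the true SDs 1.0% and 2.5 kg, for instance, the chance of no increase would be more than half under the same simulation assumptions. The unmet target has a stated consequence, so nobody applying the rule is left without an instruction.

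It would be wrong to conclude that 160 subjects and 74% joint power cannot both hold when the assumptions are right. They do hold at 1.1% and 2.7 kg; the 64–66% and 71–73% figures belong to 1.2% and 2.9 kg.

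On the population, it is true that the rule does not secure power for the FAS test. But mFAS equals FAS when no site is excluded, and FAS is never the smaller set. A site is excluded when half or more of its active-arm subjects fail the trough criterion (both of them at a site with exactly two), and a subject fails when under 75% of evaluable trough samples are quantifiable. Many excluded subjects may therefore be partly or fully treated, and a total loss of effect is the extreme case.

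**Conclusion.** No change follows. An interim that matches the planning SDs does send the trial to 45 per arm, and the check made there falls about 1–3 points short of 74% under the plan's product rule. This is a declared trade-off: up to 20 extra subjects where no site is excluded, in exchange for protection against an underestimated SD. If the planning SDs are true, the trial ends with about 80–82% joint power, above the target.

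The possible edits gain little. Dropping the margin exchanges protection for fewer subjects, which is a preference. Stating that the rule yields about 84%, 86% and 72% at the planning SDs would put figures computed at 1.2% and 2.9 kg against the wrong SDs. Showing FAS power beside mFAS power would be informative, but it alters neither the sample size nor any test.

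These conclusions rest on the plan's effective-n ratio (or the close alternative), its independence assumption for joint power, and, for the population question, assumed shares and effects at excluded sites. The trial is Phase IIa, described as not pivotal, and leaves implementation details of the re-estimation to the siDMC charter, which was not available for this check.

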8.2.10 Compliance (Medication Adherence)

The computation of compliance in the ASaT population will be based on the study medication case report form.

For each subject, percent compliance will be calculated using the following formula:

A day within the Treatment period will be considered a compliant day if the subject reports taking the prescribed number of injections from the correct vials.

The "Number of Days in Treatment Period" is defined for each subject as the total number of days from the first dose of study medication to the last day of study medication.

Summary statistics will be provided on percent compliance by treatment group.

9.0 LABELING, PACKAGING, STORAGE AND RETURN OF CLINICAL SUPPLIES

9.1 Investigational Product

The investigator shall take responsibility for and shall take all steps to maintain appropriate records and ensure appropriate supply, storage, handling, distribution and usage of investigational product in accordance with the protocol and any applicable laws and regulations.

Clinical Supplies will be provided by the Sponsor as summarized in Table 15

Clinical supplies will be packaged to support enrollment and replacement subjects as required. When a replacement subject is required, the Sponsor or designee needs to be contacted prior to dosing the replacement supplies.

Protocol/Amendment No.: 004-02

Table 15 Product Descriptions

Product Name & Potency	Dosage Form	
MK-8521: 0.6mg/mL and matching Placebo	Sterile Solution for Injection	

All other supplies not indicated in Table 15 above will be provided centrally by the Sponsor or locally by the trial site, subsidiary or designee, depending on local country operational or regulatory requirements.

For any commercially available product that is provided by the trial site, subsidiary or designee every attempt will be made to source these supplies from a single lot/batch number. The trial site will be responsible for recording the lot number, manufacturer and expiry date of any locally purchased product.

